3. INR > 2.2
4. Hepatic encephalopathy uncontrolled with outpatient medical therapy
5. Serum creatinine > 1.5 mg/dl
6. History of bone marrow depression (independent of hypersplenism associated with cirrhosis), hypersensitivity to carbamazepine or any of the tricyclic compounds such as amitriptyline, desipramine, imipramine, protriptyline or nortriptyline.
7. Evidence of a known secondary process leading to active liver disease, and for which there is compelling evidence, including but not limited to Hepatitis B, Hepatitis C, alcohol related liver disease, Wilson disease, sclerosing cholangitis, primary biliary cirrhosis
8. Alcohol intake > 30 gm/day (average from total intake over a week)

A Preliminary Study of the Efficacy and Safety of Carbamazepine in Severe Liver Disease Due to Alpha-1 Antitrypsin Deficiency

9. Evidence or history of hepatobiliary malignancy, e.g. hepatocellular carcinoma
10. Pregnancy, lactation
11. Severe cardiac or pulmonary disease felt to be a contraindication to CBZ therapy
12. History of suicide attempt
13. Potential for suicide behavior based on pre-treatment screening tools (PHQ-9 score greater than or equal to 10)
14. WBC <1,500
15. Platelets <25,000
16. Inability to take oral medication
17. Status post Transjugular Intrahepatic Portosystemic Shunt (TIPS) or scheduled to undergo procedure during trial participation

Screening visits:

At the screening visits a complete history and physical examination will be performed. Screening blood tests will be obtained to assess liver function and to verify the Child Pugh status. A pregnancy test will be done. AT phenotyping and absence of the genetic markers HLA-A*3101 and HLA-B*1502 will be confirmed. Potential subjects will be screened with the Personal Health Questionnaire-9 (PHQ-9). The PHQ-9 has been used successfully to screen adolescents over 13 years of age and adults (39). Subjects will be excluded if scoring 10 or higher on PHQ-9. An abdominal sonogram with Doppler will be performed to assess patency and directional flow of the portal and hepatic veins. Once these studies are confirmed as being consistent with the eligibility criteria arrangements will be made for the pre-treatment HVPG measurement (see below). The hepatic venous pressure gradient measurement and liver biopsy are done together as a single procedure using the transvenous route. Intravenous conscious sedation is used to carry out the procedure. Subjects will receive fresh frozen plasma if the INR >1.6 and platelet transfusion if the platelet count is <50,000 prior to the procedure to prevent bleeding as per usual clinical practice. Subjects will be carefully monitored during the procedure and in the recovery room after the procedure.

Screening Hepatic venous pressure gradient:

HVPG measurements will be obtained at the screening visits and at the 12-month follow up visit to determine the effect of the treatment. After anesthesia a venous introducer is placed in the right femoral vein or internal jugular vein by the Seldinger technique. Under fluoroscopy a 7-F balloon-tipped catheter (Boston Scientific Medi-Tech, Natick, MA) is guided into one of the major veins that drain blood from the liver into the inferior vena cava. An FDA-approved radiopaque contrast agent is infused into the catheter to be assured that it is located within the main right hepatic vein. The free hepatic vein pressure (FHVP) is then measured by recording for 60 seconds. This is done two to three times to assure that the mean pressure is reproducible. The balloon is then inflated and gently wedged so that it totally occludes the hepatic vein for the wedged hepatic vein pressure (WHVP). Once the pressure reading stabilizes the tracing is recorded for 60 seconds. This is repeated three times to assure that the mean pressure is reproducible. At the end of the measurement, contrast is injected while the balloon is inflated to check for total occlusion. The HVPG is then determined by calculating the difference between the WHVP and FHVP.

A Preliminary Study of the Efficacy and Safety of Carbamazepine in Severe Liver Disease Due to Alpha-1 Antitrypsin Deficiency

Screening Liver biopsy:

Liver biopsy provides detailed additional information regarding fibrosis and accumulation of abnormal AT in liver cells and ATZ globules.

The advantage of the current protocol, which includes HVPG measurement, is the ability to obtain 2 to 4 transvenous biopsies at the same procedure with no incremental increase in risk to the subjects (40-42). The results of the liver biopsy will in no way determine whether the subject is eligible for the trial. However, it is necessary to carry it out at the same time as the screening HVPG measurement because otherwise the subject would have to undergo 2 separate procedures (including anesthesia and transvenous catheter insertion) in the screening phase of the study

TREATMENT TRIAL

Patients who have completed the screening phase and meet the following inclusion and exclusion criteria will be eligible for the proposed interventional study. For the convenience of the study subjects, if it is verified per protocol that they do meet full inclusion criteria, the subject may be enrolled to the study and initiate therapy on the same day.

Those who completed the screening phase and are found not to be eligible will be given the option to be reevaluated in the future to determine eligibility for future studies of CBZ or other potential therapeutic agents. Patients will be eligible for the proposed CBZ trial and will be approached for informed consent to participate in the full clinical trial if following inclusion and exclusion criteria are met. They will be provided with the Carbamazepine medication guide before they give informed consent.

Inclusion criteria:

1. Met criteria for entry into the treatment trial from screening protocol
2. Age \geq 14 years to \leq 80 years of age
3. AT deficiency confirmed by ZZ or SZ phenotype and serum level $<$ 83 mg/dl (in subjects who are receiving AT replacement therapy at the time of enrollment, AT deficiency will be confirmed by ZZ or SZ phenotype and serum levels $<$ 83 mg/dl at the time of initial diagnosis and/or prior to the initiation of AT replacement therapy).
4. Subjects must have HVPG greater than or equal to 10 mm Hg unless collateral intrahepatic vessels are visualized via fluoroscopy, in which case the subject must meet all other criteria to participate in the trial.

Exclusion criteria:

1. Child Pugh Score \geq 12
2. Serum total bilirubin $>$ 5 mg/dl
3. INR $>$ 2.2
4. Hepatic encephalopathy uncontrolled with outpatient medical therapy
5. Serum creatinine $>$ 1.5 mg/dl
6. History of bone marrow depression (independent of hypersplenism associated with cirrhosis), hypersensitivity to carbamazepine or any of the tricyclic compounds such as amitriptyline, desipramine, imipramine, protriptyline or nortriptyline.

A Preliminary Study of the Efficacy and Safety of Carbamazepine in Severe Liver Disease Due to Alpha-1 Antitrypsin Deficiency

7. Evidence of a known secondary process leading to active liver disease including but not limited to Hepatitis B, Hepatitis C, alcohol related liver disease, Wilson disease, sclerosing cholangitis, primary biliary cirrhosis
8. Alcohol intake > 30 gm/day (average from total intake over a week)
9. Evidence or history of hepatobiliary malignancy, e.g. hepatocellular carcinoma
10. Pregnancy, lactation
11. Severe cardiac or pulmonary disease felt to be a contraindication to CBZ therapy
12. HLA-B*1502 positive
13. HLA-A*3101 positive
14. History of suicide attempt
15. Potential for suicide behavior based on pre-treatment screening tools (PHQ-9 score greater than or equal to 10)
16. WBC <1,500
17. Platelets <25,000
18. Inability to take oral medication
19. Status post Transjugular Intrahepatic Portosystemic Shunt (TIPS) or scheduled to undergo during trial participation

STUDY DRUG AND DRUG MANAGEMENT:

Rationale for Placebo Control:

The placebo group is designed to provide control for the effects of sample error and variability. This variability could affect liver biopsy as well as HVPG measurements and the placebo control is particularly important because of the relatively small number of subjects in the trial. In addition, the placebo control may provide insight into the tolerability of CBZ by providing natural history data for complications of AT deficiency-associated cirrhosis. Placebo will be prepared by the UPMC Investigational Drug Service (IDS) in capsules that are identical to those of the active compound CBZ.

Randomization:

Once it is determined the patient is eligible for the clinical trial, the patient will be randomized to receive a study medication that will be CBZ, the active medication, or a placebo that will appear similar to but not contain the active medication. Patients will be randomized 2:1 (CBZ: Placebo) with two patients receiving CBZ for every one patient receiving placebo. Patients will be further stratified by ongoing treatment with non-selective beta-blockers used for portal hypertension (e.g. propranolol, nadolol or carvedilol). If the patient is receiving any dose of nonselective beta-blocker prior to study entry, this may decrease portal hypertension which in turn should be associated with decreased HVPG. We want to ensure that both treatment and placebo arms have an equal number of patients receiving nonselective beta-blocker and do not plan to alter this therapy during this investigation.

The Investigational Drug Service will provide subjects with study medication sufficient to last until the next visit + 5 days extra. The UPMC Investigational Drug Service (IDS) will use Medi-dose cups for dispensing CBZ/placebo capsules, depositing one dose of medication/placebo (two capsules) in each Medi-dose cup. UPMC Investigational Drug Service (IDS) will seal and then label the Medi-dose cup with the subject's ID number and the dose of medication (or placebo). IDS will be responsible for delivering the

A Preliminary Study of the Efficacy and Safety of Carbamazepine in Severe Liver Disease Due to Alpha-1 Antitrypsin Deficiency

Medi-dose cups to subject's home address via UPS overnight shipping, and storing the remaining of the Medi-dose cups.

A Study Monitor (see below) will be the only members of the investigative team that is not blinded because the Study Monitor will be responsible for adjustments in CBZ dosage based on drug levels. The Study Monitor will consult with the sponsor-investigator and/or physician sub-investigators to determine exactly how to adjust the dosage but these consultations will be carried out without revealing the identity of the patient.

Administration and Drug Accountability:

CBZ/placebo will be administered at a maximum dose of 1200 mg/day orally for 12 months for subjects over 15 years of age and at a maximum dose of 1000 mg/day for subjects less than 15 years of age. This will involve twice daily dosing with a combination of 100 mg-extended release tablets. Extended release tablets are better tolerated, have a narrow fluctuation in drug concentration, and fewer central nervous system complications than immediate-release formulations (43). To reduce the likelihood of hypersensitivity reactions the subjects will be started on 400 mg/day in 2 doses and the dose will be increased weekly by 200 mg per day until reaching a dose of 1200 mg/day (or 1000 mg/day in subjects less than 15 years of age). A subject's dose escalation may be adjusted if deemed appropriate by the sponsor-investigator or principal investigator but it will not exceed a weekly 200 mg per day increase. Drug levels will be monitored beginning at the 4 week visit, then at each study visit to ensure that the therapeutic concentration of 4-12 ug/ml is reached but not exceeded and then maintained. CBZ will be administered orally twice a day using extended release tablets. The Study Monitor will review the results of the blood level measurements following each visit and use that information for adjustment of the dose of CBZ to maintain the therapeutic drug level. The Study Monitor will not be a member of the investigative team involved with direct patient management. The Study Monitor will not be blinded. To maintain the blinding that is essential to the study design, the Study Monitor will not communicate the actual blood level result to the subject, the subject's physician or to the sponsor-investigator team.

The Study Monitor may increase or reduce the dose of CBZ based upon the drug level, but will not increase the dose of the study drug above 1200 mg/day (or 1000 mg/day in subjects less than 15 years of age). We will only be using trough blood levels. Subjects will have to return for repeat testing if it is discovered that a determination was not done at the trough. The Study Monitor may also elect to repeat the trough blood level determination if needed to have 2 determinations before deciding on a dose adjustment. The formulation of the extended release CBZ tablets approved for commercial marketing will be supplied by Novartis and dispensed by the UPMC IDS. Patient-subjects will not be charged for CBZ or placebo.

Study Monitor

The Study Monitor will be a physician who is familiar with the side effects of CBZ. The Study Monitor will receive and review each CBZ blood level determination. Other members of the research team will monitor the clinical status and physical examination of the patients and will receive the results of the monitoring laboratory values (with the exception of CBZ levels). The Study Monitor will not communicate the actual blood level of the study medication to the patient, family, or the research team

A Preliminary Study of the Efficacy and Safety of Carbamazepine in Severe Liver Disease Due to Alpha-1 Antitrypsin Deficiency

involved with day to day management of patient-subjects participating in the clinical study. However, the Study Monitor will release the identity of the subject's study group to the Sponsor-investigator or physician sub-investigators if that information is needed for the patient's safety. The Study Monitor will recommend adjustment of the CBZ dosing based upon the blood level of CBZ.

On-treatment assessments:

During therapy, study subjects will be seen on a regular basis to assess their clinical status and to obtain standard biochemical measures of liver and renal function, cell counts, etc. Visits will also include a full history and physical examination. Specific assessments and queries will be made for any signs or symptoms of liver disease. Child-Pugh (CP) score and MELD score will be calculated at each study visit. Other than blood collection during study visits, no additional invasive testing is proposed until the week 52b visit when a repeat liver biopsy and HVPg will be obtained. The procedure for the liver biopsy and HVPg will be identical to the procedure used in the screening visit. Data will be collected from procedures undertaken as part of clinical follow up (e.g. endoscopy reports, imaging studies, etc.).

If the study subject undergoes liver transplantation during the study period, samples will be obtained at the time of surgery to provide follow up data. If a subject dies during the study period and the family consents to an autopsy, samples of liver tissue will be obtained at autopsy to provide follow up data. In these cases, follow up HVPg measurements will not be available.

Potential for suicide attempts will be monitored with the Columbia Suicide Severity Rating Scale (C-SSRS) at study visits the week of enrollment through week 52a. It is a semi-structured, clinician-administered instrument to track severity of both suicidal behavior and ideation. This measure is reliable and valid and has been used in previous clinical trials (44, 45). Patients will be withdrawn from the trial if the C-SSRS identifies suicidal ideation or behavior and then the patient will then be referred for mental health evaluation and treatment.

Study visits will be scheduled at weeks 4 (+/- 1 week), 8 (+/- 2 weeks), 18 (+/- 2 weeks), 36 (+/- 2 weeks), and 52a (+ 3 weeks) for a history and physical examination, assessment for depression and suicide behavior, biochemistry measures, and measurement of the blood level of the CBZ. Blood will also be collected at the time of enrollment and at week 52 visit for Fibrotest analysis. All female subjects of child-bearing age will undergo a urine pregnancy test on visit S2, enrollment, and at each follow up visit during the trial. The effect of CBZ treatment will also be assessed by a novel investigative test, a hepatic biomarker assay using samples that are obtained pre- and post-treatment as well as once during treatment. Study subjects may undergo MRI using Elastography within the first six months of study enrollment and at week 52 visit.

Additional visits may be scheduled, at the discretion of the Investigator, to ensure the safety and well-being of subjects. These will include a history, assessment for depression and suicide behavior, biochemistry measures, and measurement of the blood level of the CBZ. A physical exam may also be performed at the discretion of the investigator. Full list of assessments can be found on the schedule of events flow sheet.

A Preliminary Study of the Efficacy and Safety of Carbamazepine in Severe Liver Disease Due to Alpha-1 Antitrypsin Deficiency

Assessment of adherence:

Adherence will be assessed at each of the follow up visits by pill counts and patient medication diaries. Medications will only be available from the Investigational Drug Service (IDS), thus an accurate assessment of medication dispensed will be available. Subjects will be instructed to return unused medications at each visit. By pill count, medication adherence will be assessed. Adherence will be defined as intake of > 80% of the prescribed CBZ or placebo – persistent nonadherence to the study regimen may lead to discontinuation of the study for those subjects. For patients receiving CBZ, adherence will also be assessed by measuring trough CBZ levels at each visit. It is expected that the levels will be between 4 and 12 µg/ml. Standard deviations of sequential levels will also be used as a measure of adherence (46).

End of treatment assessment (week 52 visit + 1 wk):

Hepatic venous pressure gradient – see above

Liver biopsy – see above

Concomitant Medications:

CBZ may interact with other anticonvulsants, including half-life shortening when given with phenobarbital, phenytoin and primidone and half-life prolongation with valproate. Several drugs inhibit the elimination of CBZ and therefore elevate its serum levels, including erythromycin, isoniazid, triacetyloleandomycin, destropoxyphene, viloxazine, nicotinamide, verapamil and diltiazem. CBZ itself can affect the serum concentrations of other drugs, including valproate, ethosuximide, doxycycline, clonazepam, haloperidol, phenytoin and warfarin.

These drug interactions may necessitate changes in dose of CBZ or other drugs but do not prohibit the use of CBZ or other drugs while administering CBZ. These changes will be directed by the Sponsor-Investigator or sub-investigators.

ADVERSE EVENTS AND TOXICITY MANAGEMENT

Subjects will be closely monitored for the major side effects of CBZ, including allergic reaction, sedation, and bone marrow depression as well as for hepatotoxicity that could worsen the liver disease. This will include history, clinical examination and laboratory testing. Monitoring will be carried out at each study visit. In general it will not be necessary to reduce the dose of CBZ or discontinue CBZ unless there is an obvious allergic reaction, progressive hematological toxicity that includes aplastic anemia, neutropenia and/or thrombocytopenia, progressive hepatic toxicity with rising transaminases, decreasing albumin levels or prolongation of the prothrombin time, unremitting sedative effect, or CBZ levels in the toxic range.

In the event that a subject temporarily discontinues drug for any reason OR an investigator determines the a subject should temporarily hold study drug due to a clinical reason, we will reinitiate therapy based upon the following parameters;

A Preliminary Study of the Efficacy and Safety of Carbamazepine in Severe Liver Disease Due to Alpha-1 Antitrypsin Deficiency

-If study drug has been stopped for less than or equal to 5 days the subject will resume taking the previous dose.

[figure not shown]
-If study drug has been stopped for more than 5 days but less than or equal to two weeks, the subject will resume half of the previously assigned dose (if half the previous dose is unavailable, the next available formulation close to but less than half the previous dose is acceptable) for one week and return to the full previous dose 7 days later.

-If study drug has been stopped for more than 2 weeks, the sponsor-investigator along with principal investigator will determine both the dose with which the subject restarts and the appropriate dose escalation schedule.

Carbamazepine (study drug) or placebo dose alteration:

The dose of the study drug will be altered based upon the schedule below. Only the study monitor will know the serum trough level and only the study monitor will make dose adjustments for changes in the blood level. The Sponsor-Investigator and/or sub-investigators will be responsible for making adjustments in the dose of Study Medication based upon the clinical and biochemical results outlined below. If these individuals determine that the dose of study drug needs to be adjusted, the request will be made to the Study Monitor who will in turn contact the IDS to carry out the change in dose. When a dose alteration is made based on findings other than the trough blood level, comparable dose reductions will not occur in patients receiving placebo.

1. Serum trough level ≥ 12 $\mu\text{g/ml}$ (to be performed ONLY by the study monitor) See algorithm.

2. (Serum trough level ≤ 4 $\mu\text{g/ml}$ (to be performed ONLY by the study monitor)(study monitor may elect to order a repeat trough level before making a change in dosage)
 - a. No change in protocol unless prior dose reduction.

A Preliminary Study of the Efficacy and Safety of Carbamazepine in Severe Liver Disease Due to Alpha-1 Antitrypsin Deficiency

- b. If a prior dose reduction has been made by the study monitor based upon clinical or biochemical abnormality, the dose of the study medication will not be increased unless there is resolution of the clinical or biochemical finding. Increase in dose cannot be made if subject is already on dose of 1200 mg/day or, if less than 15 years of age, on a dose of 1000 mg/day
 - c. Continue “b” until trough level is in the therapeutic range

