2. WBC <1,000
 - a. Decrease dose by 50%
3. Neutrophil count <500
 - a. Decrease dose by 50%
4. Platelets < 20,000
 - a. Decrease dose by 50%
5. ALT > 500 IU/dl
 - a. Decrease dose by 50%
6. INR \geq 1.8 not corrected by 5 mg of vitamin K
 - a. Decrease dose by 50%

Guidelines for subsequent Study drug dose adjustments

Indications to discontinue CBZ

1. Child-Pugh score > 12
2. Hepatic encephalopathy uncontrolled with outpatient medical therapy
3. Total bilirubin > 7 mg/dL
4. Evidence of anticonvulsant hypersensitivity syndrome
 - a. Fever > 38.5 and
 - b. Lymphadenopathy, and
 - c. Erythematous, maculopapular, pruritic, or exfoliating rash
5. WBC <1,000 despite 2 weeks of Carbamazepine dose reduction, may resume therapy at 50% of starting dose when WBC > 3,000
6. Neutrophil count <500 despite 2 weeks of Carbamazepine dose reduction, may resume therapy at 50% of starting dose when ANC > 1,500
7. Platelet count <20,000 despite 2 weeks of Carbamazepine dose reduction, may resume therapy at 50% of starting dose when plt > 40,000
8. Hgb <8.5 mg/dl
9. INR \geq 2.5 not corrected by 5 mg of Vitamin K

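### After a short stop for a possibly drug-related skin or allergic reaction, the restart rule sets the dose by days off drug alone, which is at odds with the protocol's own slow titration

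*Combined protocol and SAP*

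**What the plan says.** The restart rule is in the combined protocol and SAP under *Adverse Events and Toxicity Management*. Its scope is wide. It opens "In the event that a subject temporarily discontinues drug for any reason" and also covers the case where an investigator decides that a subject "should temporarily hold study drug due to a clinical reason, we will reinitiate therapy based upon the following parameters". The parameters that follow are lengths of time off drug:

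- 5 days or less: "If study drug has been stopped for less than or equal to 5 days the subject will resume taking the previous dose".
- More than 5 days and up to two weeks: half the earlier dose "for one week and return to the full previous dose 7 days later".
- More than two weeks: the sponsor-investigator and principal investigator "will determine both the dose with which the subject restarts and the appropriate dose escalation schedule".

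Under *Dermatologic reactions*, subjects report redness, blisters, peeling, itching or mouth ulcers. Drug then stops at once and the subject is seen within 24 hours. The stop is permanent if the lesions look like Stevens-Johnson syndrome (SJS) or toxic epidermal necrolysis (TEN). Mild changes may be watched with no change of dose. *Indications to discontinue CBZ* adds Grade 3 or 4 allergic reactions and "Evidence of anticonvulsant hypersensitivity syndrome", defined there by fever, lymphadenopathy and rash together.

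*Administration and Drug Accountability* starts carbamazepine at 400 mg/day, and gives reduction of hypersensitivity reactions as the reason. The dose then rises weekly by 200 mg/day to 1200 mg/day (1000 mg/day under age 15). Investigators may adjust the escalation but may not exceed that weekly step.

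**The concern.** The skin-reaction text itself creates short stops. A subject with a Grade 1 or 2 drug rash may be taken off drug, examined the next day and found not to have SJS, TEN, the hypersensitivity syndrome or a Grade 3-4 reaction. If drug is resumed within two weeks, only the day-count rule supplies a dose, and it does not ask whether the reaction was drug-related. The investigators' power to choose a restart dose and re-escalation is written only for stops over two weeks.

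The protocol's *Safety* section calls allergic rash the most common reason for carbamazepine intolerance, and the trial population has cirrhosis. What is at stake is the safety of a small number of subjects at re-exposure. No efficacy analysis is affected.

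**Working it through.** There is no stated design figure to reproduce. The check sets the two dosing rules side by side.

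**Inputs.** Start 400 mg/day, weekly step and cap 200 mg/day, maximum 1200 mg/day or 1000 mg/day under 15 (*Administration and Drug Accountability*). Restart tiers (*Adverse Events and Toxicity Management*). Rash rate 4-10% (*Safety*, carbamazepine background). 20 carbamazepine subjects (*Study Design*).

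**First titration.** Weeks 1 to 5 give 400, 600, 800, 1000 and 1200 mg/day. Steps to 1200: (1200 - 400)/200 = 4 weekly steps = 28 days.

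**Restart, by dose at the time of the stop (mg/day).**

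| Previous dose | Dose after 5 days or less off | Ratio to 400 start | Dose in first week after more than 5 days, up to 2 weeks off | Then | Step | Step / 200 cap |
|---|---|---|---|---|---|---|
| 400 | 400 | 1.0 | 200 | 400 | 200 | 1.0 |
| 600 | 600 | 1.5 | 300 | 600 | 300 | 1.5 |
| 800 | 800 | 2.0 | 400 | 800 | 400 | 2.0 |
| 1000 | 1000 | 2.5 | 500 | 1000 | 500 | 2.5 |
| 1200 | 1200 | 3.0 | 600 | 1200 | 600 | 3.0 |

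Time back to 1200 mg/day is 0 or 7 days, against 28 days at first titration. The conflict is absent at 400 mg/day, grows with dose, and reaches the 1200 mg/day row only from week 5. The 1000 mg/day row is the maximum for subjects under 15.

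**Does other text supply a rule for these stops?**

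- Stops for low white cells, neutrophils or platelets resume only after a stated recovery; for white cells, "may resume therapy at 50% of starting dose when WBC > 3,000". ALT stops also have a recovery threshold, but they resume at the previous dose. So a return to the previous dose is not unique to skin reactions. What is particular to them is that no recovery condition accompanies it in the text.
- *Carbamazepine (study drug) or placebo dose alteration* requires a clinical finding to resolve, but only before a dose is raised at a low trough level after an earlier reduction. It does not govern restart after a stop.
- The restart section names allergy as a ground for action: "In general it will not be necessary to reduce the dose of CBZ or discontinue CBZ unless there is an obvious allergic reaction". It does not say how to restart afterwards.

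**Subjects concerned, as a ceiling.** 20 x 0.04 = 0.8; 20 x 0.10 = 2.0. These expected counts are for allergic rash of any severity, before the HLA exclusions. They include rashes that would meet a discontinuation criterion and mild ones that would never lead to a stop.

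**The case against.** The strongest answer is that the rule fixes the dose, not the decision. It does not limit how long a hold may last and does not compel a restart. The 24-hour examination is mandatory, extra safety visits are allowed, unresolved adverse events are followed, and treating physicians may stop study drug at any time. This stands. A reader might infer that the protocol orders rechallenge of an active rash; the documents do not support that. An unwritten recovery condition is therefore mostly missing detail. Numeric resume thresholds also suit laboratory values better than a rash, which is judged by examination.

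A second answer is that the dose multiples apply to any short stop, including missed doses, where returning to a tolerated dose is reasonable, and that re-exposure is not first exposure. This also stands for stops unrelated to the drug. It is weaker for a suspected drug reaction, because the protocol ties its low starting dose to hypersensitivity. The protocol's discussion of use in liver disease adds that lowering the dose may not avoid idiosyncratic reactions, so slow re-escalation alone would not be a sufficient safeguard.

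Third, the group is narrow, and the rash rate does not measure it. A reader might turn the 4-10% rate into a probability that the rule does harm. That does not follow: the rate covers rashes that never reach this rule, and it says nothing about how an investigator would act.

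Fourth, some material is not in the public text: a figure between the first two restart tiers, an algorithm cited for high trough levels, and whatever stands under *Guidelines for subsequent Study drug dose adjustments*. Its absence is no fault of the plan. A separate rule for skin reactions there would answer the point.

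**Conclusion.** The point holds as a minor safety improvement. Even if the investigator waits for full resolution, the written rule then prescribes the previous dose at once after 5 days or less, up to 1200 mg/day (3 times the starting dose). After a stop of more than 5 days and up to two weeks it prescribes one step of up to 600 mg/day (3 times the weekly cap). For a possibly drug-related skin or allergic reaction, that is at odds with the protocol's own titration rationale.

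The conclusion assumes that the restart doses apply as written to every temporary stop without its own resume rule, and that the unseen figure or algorithm does not set a separate restart for skin reactions. The group is at most the 0.8 to 2.0 expected allergic rashes among 20 carbamazepine subjects, and probably smaller. How often the rule would be applied unwisely cannot be estimated from the documents.

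**What to change.** In the restart rule, exempt stops for suspected skin or hypersensitivity reactions from the day-count doses. Allow restart only after the examination already required under *Dermatologic reactions* has excluded SJS, TEN and hypersensitivity syndrome, and the investigator has documented that the reaction has resolved or has a benign cause. If the reaction is possibly drug-related, the sponsor-investigator and principal investigator set the restart dose and re-escalation, as they already do after stops of more than two weeks.

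The cost is one or two sentences of protocol text. The examination is already required, so no visits, tests or subjects are added. The downside is slightly longer holds or lower exposure in perhaps one or two subjects.
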